23.1.1 ADVERSE EVENTS DESCRIPTION

The categorical variables to be described are, N and (%):

- Adverse Event Description by patient (at least once)

- If "***'Unanticipated/Other adverse event (specify below)***" is selected, the following question: "Adverse Event System Organ Class," will be shown by patient (at least one)
- Adverse Event Description by procedure (at least once)
 - If "***'Unanticipated/Other adverse event (specify below)***" is selected, the following question: "Adverse Event System Organ Class," will be shown by procedure (at least one)

23.1.2 RELATED ADVERSE EVENTS

For each Adverse Event description collected, the categorical variable to be described is, N and (%):

- According to the investigator, is this AE related to the Investigational Medical Device (JTIN) and relative procedures? Yes, certainly related / Yes, possibly related / Not related

23.1.3 ADVERSE EVENTS SERIOUS

For each Adverse Event description collected, the categorical variable to be described is, N and (%):

- Seriousness Adverse Event: Serious / Not serious

For each Serious Adverse Event description collected, the categorical variables to be described are, N and (%):

- The Adverse Event is considered serious because the patient:
 - Death
 - Life-threatening illness or injury
 - Permanent impairment of a body structure or a body function including chronic diseases
 - In-patient or prolonged hospitalization
 - Medical or surgical intervention to prevent life-threatening illness or injury or impairment
 - Fetal distress, fetal death or, a congenital abnormality, or birth defect

23.1.4 ADVERSE EVENTS LIST

A list with adverse events collected and its characteristics will be shown.

23.2 MEDICAL DEVICE DEFICIENCIES (MDD)

The categorical variables to be described are, N and (%) and Clopper-Pearson confidence intervals will be shown at 95.0% as well, for the overall population and for subgroups of patients defined according to OI Type Diagnosis (Mild/Non-deforming / Severe / Highly Severe/Progressively deforming / Lethal) as defined in section 15.6 of this document:

- Patients with at least one MDD
- Procedures with at least one MDD

23.2.1 MEDICAL DEVICE DEFICIENCIES (MDD) TYPES AND DESCRIPTION

The categorical variables to be described are, N and (%):

- Type of Device Deficiency by patient (at least once)
- Type of Device Deficiency by procedure (at least once)
- For each type of Deficiency collected Its “corresponding MDD description” will be shown

For each type of Deficiency collected, the categorical variables to be described are, N and (%):

- Did this MDD resulted in an Adverse Event for the patient? (Yes / No)
- Could surgery be completed with the device in question? (Yes / No / Not applicable)
- Was an additional surgery required following device failure? (Yes / No)

23.2.2 MEDICAL DEVICE DEFICIENCIES (MDD) LIST

A list with MDD collected and its characteristics will be shown.

24 SECONDARY OBJECTIVE

The secondary objective of the study is to evaluate the clinical safety and performance of JTIN by the three following endpoints, when the MD is used within the scope and according to the manufacturer IFU:

- **Implant survival rate: percentage of not exchanged nails up to 1 year follow-up (safety);**
- **Bone union achievement (performance);**
- **Post-treatment fracture-free survival up to 1 year follow-up (performance)**

This analysis will be performed on FAS/FAIS population.

24.1 IMPLANT SURVIVAL RATE

Implant survival rate: percentage of not exchanged nails up to 1 year follow-up.

The categorical variables to be described are, N and (%) and Clopper-Pearson confidence intervals will be shown at 95.0% as well, for the overall population and for subgroups of patients defined according to OI Type Diagnosis (Mild/Non-deforming / Severe / Highly Severe/Progressively deforming / Lethal) as defined in section 15.6 of this document:

- Number of procedures that Reason for study exit= Nail removed vs other reason

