6.2 Secondary Objectives

The secondary objective of the study is to evaluate the clinical safety and performance of JTIN by the three following endpoints, when the MD is used within the scope and according to the manufacturer IFU:

- Implant survival rate: percentage of not exchanged nails up to 1 year follow-up (safety);
- Bone union achievement (performance);
- Post-treatment fracture-free survival up to 1 year follow-up (performance)

These variables will be visually compared with data available on other devices on the market (state-of-the-art).

The sample size was calculated also to provide a significant sample for the evaluation of the following main performance endpoint: bone union achievement.

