7.4.2 Subject Identifier

Each time a patient is planned to be treated with JTIN (or has been treated with JTIN after the 1st of January 2022, i.e. retrospectively), he/she is considered potentially eligible for the study and will be screened by the clinical site team to check if they satisfy all inclusion and exclusion criteria. Only if they satisfy the criteria, they will be informed about the study and asked if they want to participate. Patients' non-opposition to the participation to the study and data collection of the single specific implantation of JTIN will be duly documented in medical records. After non-opposition documentation the site staff will create a record in the eCRF that generates a consecutive identification number (ID), related to the procedure. The ID will be registered in the patient log. If the same patient agrees to participate for another JTIN procedure: another ID will be created and a reference to the first ID is made in the dedicated field in the eCRF and in the patient log.

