10.2.7 Visit 6 - 3rd Follow-up Visit (1 year ± 1 month)

The investigator will collect information regarding changes in the concomitant medication, AEs and MDDs, if any. The investigator will also collect x-ray images of the treated limb, clinical examination, measure the Knee, Hip, Ankle ROM (as applicable) and also the weight-bearing protocol assigned to the patient. The bone consolidation will be assessed by surgeon experience and evaluating corticalization of at least three sides of the callus on the radiographs. The Gillette Functional Assessment questionnaire is collected and can performed by the investigator in presence or also by telephone or by mail with the parent (or legal representative) in a different day from the visit, according to hospital standard care.

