14 STATISTICAL ANALYSIS METHODS

The methods of analysis to be used for both objectives of the study and for description of the study variables are detailed below.

Quantitative variables will be described with measures of central tendency and dispersion: mean, median, SD (standard deviation), Q1 (first quartile) and Q3 (third quartile), minimum and maximum. Qualitative variables will be described using absolute and relative frequencies.

In the descriptive analysis of qualitative variables, two percentage columns will be presented, total percentage (%) and valid percentage (% valid), that are respectively, the percentage over the sum of valid responses plus missing values and the percentage over the total of valid responses.

Clopper-Pearson confidence intervals at 95.0% will be shown for the primary and secondary objectives.

For time-to-event variables (i.e. fracture free-survival) will be analysed using the Kaplan-Meier method. The median and the 95% CI as well as the number of events and patients censored will be provided. Error standard will be estimated per the method Greenwood (Greenwood, 1926). KM graphs will be presented along with the number of case-at-risk at exact time points.

Change in Gillette Functional Assessment Questionnaire from Screening to 1 year follow up will be analysed by means of descriptive statistics as a continuous variable. Comparisons will be performed by means of paired t-test (parametric) or Wilcoxon (non-parametric) depending on the distribution of the sample.

These tests will be used in all bilateral cases and with a level of significance of 0.05. In cases where a p-value less than 0.05 appears, it refers to the existence of statistical significance.

No imputation for missing data will be considered.

No adjustment for multiple comparisons will be performed.

Data will be analysed using SPSS v29.0 or later.

Interim Analysis: No interim analysis is planned.

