16.1 DEVICE APPLICATION SURGERY

The descriptive statistic (Mean, SD, Median, Q₁, Q₃, Min, Max) will be shown for the following continuous variable:

- Duration of the surgery (hours)

The categorical variables to be described are, N and (%):

- Was other fixation device removed from the same bone during this surgery? (Revision surgery) (Yes / No), if yes:
 - What device was removed? :
 - JTIN nail
 - Other telescopic nail
 - Non-telescopic rigid nail
 - Elastic nails
 - Plate
 - Screws
 - Other (a list will be shown)

The descriptive statistic (Mean, SD, Median, Q₁, Q₃, Min, Max) will be shown for the following continuous variables:

- Female rod diameter mm
- Diameter mm x 10
- Nail length mm
- Number length

The categorical variables to be described are, N and (%):

- Nail Product Code
 - 99-67735100
 - 99-67735120
 - 99-67735130
 - 99-67735140
 - 99-67735150
 - 99-67740130
 - 99-67740155
 - 99-67740180
 - 99-67740205
 - 99-67740230
 - 99-67745160
 - 99-67745175
 - 99-67745190
 - 99-67745205
 - 99-67745230
 - 99-67750250
 - 99-67750275
 - 99-67750300
 - 99-67750325
 - 99-67750350
 - 99-67760250
 - 99-67760275
 - 99-67760300
 - 99-67760325
 - 99-67760350
- If 'Nail Product Code' is equal to '99-67735100' answer this question:
 - Nail batch number (B1783051 / B2641703 / B3009814)
- If 'Nail Product Code' is equal to '99-67735120' answer this question:
 - Nail batch number (B1782950 / B2641683 / B2742622 / B4443378)
- If 'Nail Product Code' is equal to '99-67735130' answer this question:
 - Nail batch number (B1786577 / B1788041 / B2641704 / B2815658)
- If 'Nail Product Code' is equal to '99-67735140' answer this question:
 - Nail batch number (B1786575 / B1788107 / B2641702 / B3478907 / B3549910)
- If 'Nail Product Code' is equal to '99-67735150' answer this question:

- Nail batch number (B1783016 / B1788040 / B2641701 / B2992850 / B4443379)
- If 'Nail Product Code' is equal to '99-67740130' answer this question:
 - Nail batch number (B1786576 / B1788109 / B1803399)
- If 'Nail Product Code' is equal to '99-67740155' answer this question:
 - Nail batch number (B1782964 / B1788110 / B1808958 / B2598629)
- If 'Nail Product Code' is equal to '99-67740180' answer this question:
 - Nail batch number (B1786609 / B1788104 / B1808957 / B2598628 / B2959917 / B3013876 / B3584086 / B3935695)
- If 'Nail Product Code' is equal to '99-67740205' answer this question:
 - Nail batch number (B1786622 / B1788105 / B2588616 / B3560929 / B4443313)

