21.1 VISIT INFORMATION

The descriptive statistic (Mean, SD, Median, Q₁, Q₃, Min, Max) will be shown for the following continuous variable:

- Time from surgery to 3er follow up visit (months) (calculated as 3er follow visit Date minus date of surgery)

The categorical variable to be described is, N and (%):

- Time from surgery to 3er follow up visit (months) within the time windows estimated in the protocol (23-25 months)? (Yes / No)

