22 STUDY EXIT VISIT

This analysis will be performed on FAIS population.

The categorical variables to be described are, N and (%):

- Reason for study exit
 - Subject completed protocol last visit
 - Nail removed
 - Subject does not meet inclusion criteria (a list will be shown)
 - Subject withdrew consent
 - Subject withdrawn by Investigator (a list will be shown)
 - Subject Death
 - Lost to follow-up
 - Subject had an AE that does not permit the continuation of the study (specify nr. of AE: a list will be shown)
 - Other Reason (a list will be shown)

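### SAP 24.1 scores implant survival from the exit reason, so nails lost before 1 year count as not exchanged and removal without exchange counts as failure

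*SAP*

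**What the plan says.** Protocol 6.2 sets the endpoint as "Implant survival rate: percentage of not exchanged nails up to 1 year follow-up (safety"). Protocol 12.2.1 and the opening line of SAP 24.1 define it the same way.

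SAP 24.1 then names one variable, "Number of procedures that Reason for study exit= Nail removed vs other reason", to be reported with N, % and a Clopper-Pearson interval, overall and by OI group. SAP 22 lists the possible exit reasons. Besides completion and nail removal they include loss to follow-up, withdrawn consent, withdrawal by the investigator, death, and "Subject had an AE that does not permit the continuation of the study".

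For the primary endpoint, SAP 23.1 reports procedures with at least one certainly or possibly related AE. SAP 13 defines the implant-level set (FAIS) as all JTIN applications in FAS subjects and sets no minimum follow-up. SAP 14 reports two percentages for categorical variables, "the percentage over the sum of valid responses plus missing values and the percentage over the total of valid responses", and rules out imputation. Kaplan-Meier is specified for fracture only (SAP 14 and 24.3).

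**The concern.** Exchange and removal are different events, and an exit reason is not a 1-year status. The rule in SAP 24.1 treats each pair as the same.

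- **Nails of unknown status become survivors.** Lost and withdrawn nails fall into the other-reason class together with completers.
- **Removal without exchange becomes a failure**, although the endpoint is exchange.
- **The two percentage columns do not help.** Lost to follow-up is a valid response on the exit form, and having no AE record is not a missing value. Neither case leaves the denominator.

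At stake are the study's two named safety endpoints (Protocol synopsis). Protocol 6.2 also plans a visual comparison of implant survival with other marketed devices. A rate built on another definition, with losses counted as successes, is not like for like.

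**Working it through.** **1. The plan's own figures.** Inputs from Protocol 12.3: AE rate 31%, ceiling 60%, 20 evaluable procedures, 20% drop-out or non-evaluable. The Clopper-Pearson upper limit with x = 0.31n is 60.5% at n = 14 and 59.4% at n = 15, so 15 reproduces. 20/(1 - 0.20) = 25 also reproduces. The 20 evaluable procedures are a planning number only. The SAP defines no evaluable set, and its percentages use all implanted nails.

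**2. How SAP 24.1 classifies each exit**

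| Exit situation | Scored by SAP 24.1 | Under the defined endpoint |
|---|---|---|
| Completed last visit, nail in place | survived | not exchanged |
| Nail removed and replaced | failed | exchanged |
| Nail removed, not replaced | failed | not exchanged |
| Lost or withdrawn before 1 year | survived | unknown at 1 year |
| Death, nail in place | survived | not exchanged |

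The third and fourth rows are wrong.

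**3. Primary endpoint under loss.** The documents do not give the timing of AEs or of loss, so these are scenarios with non-informative loss. Let p be the true 1-year rate and L the proportion lost at times spread evenly over the year.

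- Constant hazard: h = -ln(1 - p), and the chance of an event before loss is u = 1 - p/h. The reported rate is (1 - L)p + Lu.
  - For p = 0.31: h = 0.371 and u = 0.165.
  - L = 0.20: 0.248 + 0.033 = 28.1%.
- Half of AEs at surgery, the rest even over the year (AEs are collected from surgery on, Protocol 10.2.2): (1 - L)p + L(p/2 + p/4).
  - L = 0.20: 0.248 + 0.0465 = 29.5%.
- Bound, with every loss preceding any AE: (1 - L)p = 24.8%.
- L = 0.10 with spread loss gives 29.5-30.2%. L = 0.05 gives 30.3-30.6%.

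**4. Against sampling error.** 0.281 × 25 ≈ 7, and 7/25 = 28.0% has a 95% interval of 12.1-49.4%, a width of 37.3 points. 0.31 × 25 ≈ 8, and 8/25 = 32.0% has 15.0-53.5%. Both upper limits are below 60%.

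**5. Implant survival under loss.** The documents give no 1-year exchange rate. Protocol 11.1.6 quotes literature surgical revision of 22.22-50%, which is a different event with no stated time point, so true survival is assumed. The constant-hazard formula is applied to the failure proportion.

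| Assumed true survival | Reported at L = 0.20 | Shift (points) |
|---|---|---|
| 95% | 95.5% | +0.5 |
| 90% | 91.0% | +1.0 |
| 80% | 81.9% | +1.9 |
| 77.8% | 79.9% | +2.1 |

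**6. Removal without exchange.** Each one lowers reported survival by 1/25 = 4 points. As an illustration with assumed counts, take 25 nails with 4 removals, 2 of them without replacement. The SAP rule gives 21/25 = 84.0%. The defined endpoint on the same denominator gives 23/25 = 92.0%.

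**7. Precision cost of the censored estimate.** I simulated 20,000 studies of 25 nails with p = 0.31 and 20% spread loss. Under constant hazard the crude percentage averages 28.1% (SD 8.9 points) and 1 - Kaplan-Meier averages 31.0% (SD 9.8). With half of AEs at surgery the figures are 29.6% (SD 9.1) and 31.1% (SD 9.6).

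**The case against.** The strongest reply is that the information is already planned. SAP 22 tabulates every exit reason on the FAIS, and SAP 24.1 only collapses that table. A reader might infer from SAP 24.1 alone that follow-up behind implant survival is hidden. It is not: overall completers, removals and losses can be recovered. What stands is that the reported rate, its interval and the OI subgroup rates still rest on the wrong classification, and that no such table is tied to the primary endpoint.

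A second reply is that Protocol 7.2 ends a case at implant removal and every exchange involves a removal, so removal is a conservative proxy. That explains the choice, but the proxy is not the defined endpoint.

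Third, the primary-endpoint part is an inference. The SAP does not say how early losses are counted. The result follows from the all-implants denominator without censoring, and a percentage of procedures is what the protocol asks for.

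Other stronger readings are also unsupported:

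- **Death is left unhandled.** It is not: under SAP 24.1 it is an other reason, which fits a nail not exchanged. It needs a rule only once a time-to-event estimate is added.
- **Exchanges prompted by an AE are scored as survival.** This is only a possibility. It requires that the exit form accepts a single reason, which is not stated, and that the AE code is chosen over the dedicated nail-removed code.
- **The AE rate would be cut by a fifth.** The 24.8% figure is a bound that needs every loss to precede any AE.

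**Conclusion.** The point holds for implant survival as written: the variable in SAP 24.1 does not measure the endpoint it defines. For the primary endpoint it holds by inference.

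The effect is modest. With spread, non-informative loss of 5-20% the AE rate is understated by 0.4-2.9 points, and at 20% loss by at most 6.2. Loss raises implant survival by about 0.5-2 points at 20% for true survival of 95-78%, while each removal without exchange lowers it by 4, so the net direction is unknown. Loss may be below 20%: that figure includes non-evaluable procedures (Protocol 12.3), patients likely to be lost are excluded (Protocol 8.2), and part of the cohort is retrospective (Protocol 10.1). No test is affected and the reading against 60% stands. The intervals treat nails as independent although a subject may contribute one to four (Protocol 12.3), which is a separate matter.

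A related inconsistency limits the check on 1-year follow-up. SAP 21.1 tests the third follow-up visit "within the time windows estimated in the protocol (23-25 months"), whereas the protocol has "3rd Follow-up Visit (1 year ± 1 month"). SAP 21.1 also summarises the actual time to that visit, so follow-up among attenders is visible, but the in-window flag follows a window the protocol does not contain.

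Severity: minor to should-fix.

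**What to change.** - **Event.** In SAP 24.1, define the event as nail exchange with its date, taken from surgery, AE and exit data rather than the exit reason alone. Report removal without exchange on its own line.
- **Estimates.** Keep the protocol's percentages with Clopper-Pearson intervals. Beside them give a 12-month Kaplan-Meier estimate for implant survival and for the first certainly or possibly related AE. Write out the censoring date (last contact) and the handling of death. SAP 24.3 cannot simply be copied, because it reports the number censored but defines time only for events.
- **Counts.** Next to each percentage show the number followed to 1 year and the number lost without an event.
- **Window.** Reconcile SAP 21.1 with Protocol 10.2.7.

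The cost is a few sentences, two estimates and two counts per endpoint. AE dates are already recorded (Protocol 11.1.10). When an enrolled JTIN replaces a JTIN, the exchange date is the later case's surgery date. The surgery form asks "Was other fixation device removed from the same bone during this surgery? (Revision surgery") with JTIN nail as one answer, and for a repeat procedure "another ID will be created and a reference to the first ID is made in the dedicated field in the eCRF". When the replacement is another device, the sponsor must confirm that the date is available. Correcting for loss makes the rates slightly less favourable and the intervals slightly wider. Separating out removal without exchange would raise implant survival.

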24.2 BONE UNION ACHIEVEMENT

The categorical variables to be described are, N and (%) and Clopper-Pearson confidence intervals will be shown at 95.0% as well, for the overall population and for subgroups of patients defined according to OI Type Diagnosis (Mild/Non-deforming / Severe / Highly Severe/Progressively deforming / Lethal) as defined in section 15.6 of this document:

- Number of procedures that reached a satisfactory bone consolidation in any visit (considering at the first visit in which the answer is “Yes” in “Has the bone reached a satisfactory consolidation?” variables in removal or bone consolidation visits)
- Number of patients that reached a satisfactory bone consolidation in any visit or procedure (considering at the first visit in which the answer is “Yes” in “Has the bone reached a satisfactory consolidation?” variables in removal or bone consolidation visits)

The descriptive statistic (Mean, SD, Median, Q₁, Q₃, Min, Max) will be shown for the following continuous variable, for the overall population and for subgroups of patients defined according to OI Type Diagnosis (Mild/Non-deforming / Severe / Highly Severe/Progressively deforming / Lethal) as defined in section 15.6 of this document:

- Time to full a satisfactory bone consolidation from surgery (months), per procedure, considering at the first visit in which the answer is “Yes” in “Has the bone reached a

satisfactory consolidation?" variables in removal or bone consolidation visits. Calculated as date of first consolidation minus date of surgery.

A list with bone consolidation variables will be shown.

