12.2.2 Evaluation of Efficacy

The first efficacy endpoint (Bone union achievement) will be analyzed reporting the number and the proportion of procedures with bone union achieved (Success) together with the relative 95% confidence interval.

The second efficacy endpoint (Post-treatment fracture-free survival) will be analyzed reporting the number and the proportion of procedures with fracture(s) occurred in the treated bone up to 1 year follow-up together with the relative 95% confidence interval.

The cumulative freedom from fracture will be also evaluated using Kaplan-Meier (KM) method, the degree of uncertainty will be expressed with 95% confidence limits (calculated per the method proposed by Greenwood) and a KM graph will be presented along with the number of case-at-risk at exact time points.

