21.4 RADIOGRAPHIC IMAGES

The categorical variables to be described are, N and (%):

- Radiographic image: Medio-Lateral projection (ML)

- Radiographic image: Antero-Posterior projection (AP)
- Number of additional radiographic images to upload (1 / 2)

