24.4 WEIGHT BEARING GRADE

The categorical variables to be described are, N and (%) and Clopper-Pearson confidence intervals will be shown at 95.0% as well, for the overall population and for subgroups of patients defined according to OI Type Diagnosis (Mild/Non-deforming / Severe / Highly Severe/Progressively deforming / Lethal) as defined in section 15.6 of this document:

- Number of procedures that reached a Full weight-bearing (FWB) from surgery in any visit
- Number of Patients that reached a Full weight-bearing (FWB) from surgery in any visit or procedure

The descriptive statistic (Mean, SD, Median, Q₁, Q₃, Min, Max) will be shown for the following continuous variable, for the overall population and for subgroups of patients defined according to OI Type Diagnosis (Mild/Non-deforming / Severe / Highly Severe/Progressively deforming / Lethal) as defined in section 15.6 of this document:

- Time to Full weight-bearing from surgery (months), per procedure, considered at the first date in which the answer is "Full weight-bearing (FWB)" in "Weight bearing protocol assigned" variables. Calculated as date of the first visit of Full weight-bearing minus date of surgery.

A list with Weight bearing grade variables will be shown.

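### SAP 24.2 labels bone union as reached at any visit but derives it from Visits 3 and 4 only, so a bone that first unites later is scored as not united

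*SAP*

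**What the plan says.** SAP 24.2 (Bone union achievement) gives a count with a Clopper-Pearson interval, the "Number of procedures that reached a satisfactory bone consolidation in any visit", and a matching patient-level count. The bracket after each defines the source: the first Yes on the item asking whether consolidation has been reached, taken from the "variables in removal or bone consolidation visits". The same restriction is written into the continuous variable, "Time to full a satisfactory bone consolidation from surgery (months), per procedure". The section ends with a listing of the consolidation variables.

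That item is on the Visit 3 form (SAP 18.2) and the Visit 4 form (SAP 19.2). At Visits 5 and 6 (SAP 20.2 and 21.2) the question is whether consolidation has been *maintained*, and SAP 24.2 does not use it.

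Protocol 12.2.2 asks for the number and proportion of procedures with union achieved and a 95% confidence interval, and names no visit. Protocol 10.2.7 says of the 1-year visit: "The bone consolidation will be assessed by surgeon experience and evaluating corticalization of at least three sides of the callus on the radiographs". Protocol 10.2.4 and 10.2.5 set the same criterion for Visits 3 and 4. Protocol 6.2 calls this the "main performance endpoint: bone union achievement".

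**The concern.** The label and the derivation disagree within one line. A reader of the report would take the rate to mean union at any time in the year of follow-up. What is computed is union recorded by Visit 4, nominally 5 months (window 3 to 7 months).

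Two results are affected, in opposite directions:

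- **The rate.** A late union counts as a failure, so the rate is too low for what its label says.
- **Time to consolidation.** A late union has no value, so the slowest bones drop out and the summary is biased short.

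The union assumption (80%, the literature mean) raised the sample from 15 to 20 procedures in Protocol 12.3. Protocol 6.2 says the secondary variables will be compared visually with data on other devices. This is therefore the figure that will be set beside published rates.

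**Working it through.** **1. The plan's own figures.** 20 / (1 − 0.20) = 25 procedures, as stated in Protocol 12.3. For the 15 procedures, the two-sided 95% Clopper-Pearson upper limit at a rate of 31% (allowing a non-integer count) is 59.4% at n = 15 and 60.5% at n = 14. So 15 is the smallest n that keeps the limit at or below 60%. The step to 20 for 80% union cannot be re-derived, because no precision criterion is given. None of these figures depends on the point at issue.

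**2. Which answers reach the endpoint.**

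| Visit | Consolidation item | Protocol states the three-sided callus criterion | Used in SAP 24.2 |
|---|---|---|---|
| 3 (2 months) | reached | yes (10.2.4) | yes |
| 4 (5 months) | reached | yes (10.2.5) | yes |
| 5 (9 months) | maintained | no (10.2.6) | no |
| 6 (1 year) | maintained | yes (10.2.7) | no |

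A procedure answered No or Partially at Visits 3 and 4 cannot become a success, whatever Visits 5 and 6 show.

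**3. Is late union foreseen?** Yes. The Visit 5 and 6 forms ask for an explanation when consolidation has not been reached, and for any change since the previous visit. Protocol 11.1.5 lists delayed union as a possible device effect. Protocol 11.1.6 gives 8.47% to 36% for non-union and delayed union together. The two are not separated, so no late-union rate follows from the documents.

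**4. The same phrase elsewhere.** SAP 24.4 gives the "Number of procedures that reached a Full weight-bearing (FWB) from surgery in any visit" with no visit restriction.

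**5. Effect on the rate.** One procedure is 1/20 = 5.0 points, or 1/25 = 4.0 points. Assume that 16 of 20 unite by 1 year (80%) and that k of those first unite after Visit 4:

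| k (assumed) | Reported under SAP 24.2 | 95% Clopper-Pearson interval |
|---|---|---|
| 0 | 16/20 = 80% | 56.3% to 94.3% |
| 1 | 15/20 = 75% | 50.9% to 91.3% |
| 2 | 14/20 = 70% | 45.7% to 88.1% |

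**6. Effect on time to consolidation.** Assume 5 bones united at Visit 3 and 10 at Visit 4, placed at the nominal 2 and 5 months.

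- SAP rule: (5 × 2 + 10 × 5) / 15 = 60/15 = 4.0 months.
- With one late union at 9 months: 69/16 = 4.3 months.
- With one late union at 12 months: 72/16 = 4.5 months.

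The median is 5 months in all three cases. The maximum rises from 5 to 9 or 12 months.

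**The case against.** The strongest reply is that union by Visit 4 is what was meant. Visit 4 is titled as the bone consolidation assessment, and its form says consolidation is expected by then. The later forms switch to asking whether it was maintained. Protocol 6.2 gives union no 1-year horizon, unlike the other two secondary endpoints. The bracket is explicit and used consistently, so a programmer has only one derivation to follow.

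That reading is plausible, but it does not rescue the text: if it is right, the label is wrong. It is also not the only reading. The Visit 5 and 6 forms repeat that consolidation is expected, so that remark does not single out Visit 4. Protocol 7.2 allows each case to be evaluated to the last visit, or to implant removal if earlier.

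Some qualifications stand:

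- A procedure with no answer at Visits 3 and 4 is missing, not failed, and falls outside the valid percentage.
- At patient level, another bone united by Visit 4 can mask a late one.
- Visit timing follows site practice, so a late Visit 4 may catch some slow unions.
- Late answers are tabulated by visit, so they are not lost to a careful reader.
- SAP 21.4 tabulates the 1-year images, not a reading of union. It shows that films are collected and no more.
- Protocol 10.2.6 describes neither a radiograph nor a consolidation assessment at Visit 5. The X-ray row of the Protocol 4.1 schedule has as many marks as the clinical examination row, which suggests a film there. The column alignment is not certain in the text reviewed, so a Visit 5 Yes needs a check.

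**Conclusion.** The concern holds. As written, SAP 24.2 carries a label wider than its derivation, and any bone recorded as not united at Visits 3 and 4 that unites later is a failure in the procedure-level rate and absent from the time summary. The size is 5 points per late union at 20 procedures and 4 points at 25. The intervals above rest on an assumed 16 of 20 united by 1 year, and the mean times on an assumed split between visits. The actual number of late unions is unknown and may be zero.

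The mismatch is certain; which horizon was intended is not. The documents also do not give the horizon of the 80% literature mean, so they cannot show which rate is the fairer comparator. The endpoint is secondary and descriptive, so no pass/fail decision changes. The correction should still be made before the analysis, so that the horizon is not chosen after the results are seen.

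**What to change.** Amend SAP 24.2 in all three places where the bracket appears (procedure count, patient count, time to consolidation), so that count and time follow one rule:

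1. Accept the first Yes at any visit through 1 year.
2. Treat a Yes on the *maintained* item at Visit 5 or 6 as reached when the earlier answers were No or Partially.
3. Flag cases where an earlier form is missing, or where a Visit 5 Yes has no radiograph.
4. Report union by Visit 4, with its interval, as a second line.

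If union by Visit 4 is the intended endpoint, replace the any-visit label with that and show union by 1 year, with its interval, beside it.

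The cost is SAP wording and one derivation rule. No new data are needed. The drawback is that some Visit 5 answers may rest on clinical judgement without a film, which is the reason for the flag.
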